#### CONFIDENTIAL AND PROPRIETARY

This document contains information that is confidential and proprietary to Smith & Nephew PLC and Smith & Nephew, Inc. and is intended for use only by Smith+Nephew and its manufacturer. It shall not be reproduced or copied in whole or in part, nor shall the contents be disclosed by any means without prior written permission from Smith+Nephew, nor shall anyone make any use of it that is contrary to the expressed or implied wishes of Smith+Nephew.

TMP-CD-05-01 Clinical Protocol - Device - Revision D; SOP-CD-05 Clinical Protocol

Clinical Protocol	Study Number: CORI.2019.06
A Prospective, Multi-center, Randomized Controlled Study to Evaluate the Safety and Effectiveness of REAL INTELLIGENCE™ CORI™ in unicondylar knee arthroplasty (UKA) Procedure	Version: 4.0-Master, 07 Sep 2022
	Page: 52 of 167

- Any other significant reason identified by the Investigator

For each case, the information will be recorded in the subject's source document and the electronic Case Report Form (eCRF), detailing circumstances leading to the withdrawal.

Subjects who withdraw or are withdrawn by the investigator cannot be re-enrolled in the study. Withdrawn subjects will not be replaced.

If at any point during the study, the unicondylar prosthesis needs to be revised for any reason the following will apply: Subjects shall continue to have follow-up visits in order to monitor the subject's health status. Potential data following the revision surgery will not be included as study data but presented separately as safety data.

For minor revisions, where not the whole knee implant system is replaced (e.g. replacement of inserts) the subject shall continue with the study specific schedule and data will be presented.

### **7.8.3 Subject's Withdrawal of Consent to Participate in the Study**

Study participation is voluntary, and subjects may withdraw from the study at any time. Where subjects withdraw consent, the Investigator should make a reasonable effort to ascertain the reason(s), while fully respecting the subject's right to privacy. The reason for withdrawal will be recorded in the eCRF and source documents.

### **7.8.4 Use of Data Following Withdrawal**

In cases where the subject withdraws consent, the data collected up to the point of withdrawal may be used, but no additional data for that subject may be collected.

## 8 STUDY DESIGN

### 8.1 STUDY DESIGN

This study is a prospective, multi-center, randomized controlled, non-blinded follow-up study to evaluate the use of CORI in UKA procedure in achieving post-operative leg alignment. Up to 8 sites will participate within Australia, China (Hong Kong), New Zealand, South Korea, and China Mainland.

The pre-randomized stage of the study will comprise of at least 5 subjects enrolled and treated with CORI directly in order to fulfil the learning needs of the surgeons. Subjects who will comprise the randomized stage of the study will be enrolled and randomized into one of two (2) groups, as shown in Table 8.1-8-1.

All groups are treated with knee arthroplasty with a S+N Knee Implant System. (The implant system will be selected according to the registration status in each country).

**Table 8.1- 8-1 Overview of Study Groups**

Surgery	Knee Implant system	Surgical Technique (Groups)	Number of Subjects
Primary UKA	S+N UKA Implant System (Journey II	CORI	70
	Unicompartmental Knee System, Journey Uni)	Conventional manual instrumentation	70

CONFIDENTIAL AND PROPRIETARY

This document contains information that is confidential and proprietary to Smith & Nephew PLC and Smith & Nephew, Inc. and is intended for use only by Smith+Nephew and its manufacturer. It shall not be reproduced or copied in whole or in part, nor shall the contents be disclosed by any means without prior written permission from Smith+Nephew, nor shall anyone make any use of it that is contrary to the expressed or implied wishes of Smith+Nephew.

TMP-CD-05-01 Clinical Protocol - Device - Revision D; SOP-CD-05 Clinical Protocol

Clinical Protocol	Study Number: CORI.2019.06
A Prospective, Multi-center, Randomized Controlled Study to Evaluate the Safety and Effectiveness of REAL INTELLIGENCE™ CORI™ in unicondylar knee arthroplasty (UKA) Procedure	Version: 4.0-Master, 07 Sep 2022
	Page: 54 of 167

### Figure 8.1-8-1 Study Recruitment Timeline

The study is expected to enroll all subjects within a 12-month timeframe. Subjects will be followed-up for a time period of 12 months after surgery. Figure 8.1-8-1 details the Study Recruitment timeline.

This study is being conducted in parallel to a global cohort study titled: "A Prospective, Multi-center Study to Evaluate the Safety and Effectiveness of REAL INTELLIGENCE™ CORI™ in unicondylar knee arthroplasty (UKA) and total knee arthroplasty (TKA) Procedures" (Protocol ID: CORI.2019.07). The study data may be combined for analysis. Further details are described in Section 10 Statistical Design and the Statistical Analysis Plan (SAP).

Figure 8.1-8-2 details the different steps of study conduct from screening to enrollment and follow-up.

[figure not shown]
Subjects may be assigned a subject ID, but then not enrolled in the study (e.g. did not receive the study device or decided not to participate in the study).

**Figure 8.1-8-2 Study Flowchart**

## 8.2 ALLOCATION AND BLINDING

### 8.2.1 Treatment Allocation

Subjects will be randomly assigned to the CORI navigational or conventional manual instrumentation groups according to a balanced randomization procedure using a 1:1 allocation ratio. To ensure balanced group assignment within each investigational site, a block (by investigational site) randomization schedule will be generated. Only sites will be included that are willing to perform both, CORI Navigated and conventional instrumentation UKA procedures. Subjects who satisfy all inclusion and exclusion criteria will be randomized in a 1:1 randomization allocation ratio. The block size should be sufficiently small to allow approximately equal allocation of subjects in each group should the study be terminated prematurely whilst also being large enough so as the next treatment cannot be guessed.

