### CONFIDENTIAL AND PROPRIETARY

This document contains information that is confidential and proprietary to Smith & Nephew PLC and Smith & Nephew, Inc. and is intended for use only by Smith+Nephew and its manufacturer. It shall not be reproduced or copied in whole or in part, nor shall the contents be disclosed by any means without prior written permission from Smith+Nephew, nor shall anyone make any use of it that is contrary to the expressed or implied wishes of Smith+Nephew.

Clinical Protocol	Study Number: CORI.2019.06
A Prospective, Multi-center, Randomized Controlled Study to Evaluate the Safety and Effectiveness of REAL INTELLIGENCE™ CORI™ in unicondylar knee arthroplasty (UKA) Procedure	Version: 4.0-Master, 07 Sep 2022
	Page: 47 of 167

- 1 Subject receives a UKA on the index joint as a revision for a previously failed surgery, or need for complex implants, or any other implant than a standard UKA (e.g. stems, augments, or custom made devices).
- 2 Subject has been diagnosed with post-traumatic arthritis
- 3 Subject receives simultaneous bilateral UKA OR a unilateral UKA with contralateral TKA.
- 4 Subject has one or more of the following arthroplasties that are not fully healed and well-functioning, as determined by the investigator:
  - Contralateral primary TKA or UKA, however, the subject can only have one knee enrolled in the study.
- 5 Subject does not understand the language used in the Informed Consent Form.
- 6 Subject does not meet the indication or is contraindicated for UKA according to specific S+N knee system's Instructions for Use (IFU).
- 7 Subject has active infection or sepsis (treated or untreated).
- 8 Subject is morbidly obese with a body mass index (BMI) greater than 40.
- 9 Subject is pregnant or breast feeding at the time of surgery.
- 10 Subject, in the opinion of the Investigator, has advanced osteoarthritis or joint disease at the time of surgery and was better suited for an alternate procedure.
- 11 Subject currently enrolled in another orthopedic clinical trial study.

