### 8.2.2 Blinding

The study is non-blinded.

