#### **8.5.2 Prospective Consecutive Enrolment**

Subjects meeting all inclusion/exclusion criteria will be randomly allocated to one of two treatment groups (CORI Navigational versus conventional manual instrumentation) in a 1:1 allocation ratio. Blocked randomization to balance this allocation ratio by investigational site and overall will be implemented through a

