#### CONFIDENTIAL AND PROPRIETARY

This document contains information that is confidential and proprietary to Smith & Nephew PLC and Smith & Nephew, Inc. and is intended for use only by Smith+Nephew and its manufacturer. It shall not be reproduced or copied in whole or in part, nor shall the contents be disclosed by any means without prior written permission from Smith+Nephew, nor shall anyone make any use of it that is contrary to the expressed or implied wishes of Smith+Nephew.  
TMP-CD-05-01 Clinical Protocol - Device - Revision D; SOP-CD-05 Clinical Protocol

Clinical Protocol	Study Number: CORI.2019.06
A Prospective, Multi-center, Randomized Controlled Study to Evaluate the Safety and Effectiveness of REAL INTELLIGENCE™ CORI™ in unicondylar knee arthroplasty (UKA) Procedure	Version: 4.0-Master, 07 Sep 2022
	Page: 59 of 167

network-based randomization system. A randomization number is allocated only when subjects have signed the Informed Consent Form and satisfy all study eligibility criteria.

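### Block size alone cannot stop the next allocation being guessed in an open trial blocked by site; the protocol should specify randomly varying, undisclosed block sizes

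*Protocol*

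**What the plan says.** Section 8.2.1 of the protocol sets up site-stratified blocking: "To ensure balanced group assignment within each investigational site, a block (by investigational site) randomization schedule will be generated". It then places two demands on the block size. For balance: "The block size should be sufficiently small to allow approximately equal allocation of subjects in each group should the study be terminated prematurely". For unpredictability, the size must also be "large enough so as the next treatment cannot be guessed". No number is given, and the text neither requires a constant size nor provides for varying sizes or for keeping them from sites.

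Section 8.2.2 says: "The study is non-blinded". Section 8.5.2 repeats the blocking ("Blocked randomization to balance this allocation ratio by investigational site and overall will be implemented") and describes release through a "network-based randomization system. A randomization number is allocated only when subjects have signed the Informed Consent Form and satisfy all study eligibility criteria".

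Some entry criteria rest on the investigator's opinion. Exclusion 10 in section 7.3 removes a subject who, in that opinion, "has advanced osteoarthritis or joint disease at the time of surgery and was better suited for an alternate procedure". Randomisation takes place at the pre-operative visit (section 9.1.2), whose window runs from 90 days before surgery to the day itself (Table 9.1.1-9-1).

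SAP section 6.2 repeats the 1:1 ratio and adds nothing on blocks.

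**The concern.** The only protection named against guessing is the size of the block. In an open trial the site knows which technique each of its earlier subjects received, so it can count the allocations left in the current block if it knows the size. The last place in every completed 1:1 block is then certain, and sometimes the places before it are too. Enlarging the block makes this less frequent but works against the balance demand in the same sentence.

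What is at stake is selection before randomisation. An investigator who foresees the next allocation can, without intending to, judge a borderline knee unsuitable under exclusion 10, or randomise one waiting subject before another. The primary endpoint is alignment within ±3° of target, and it is plausible that harder knees miss that target more often. Any such selection would fall on the main comparison.

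**Working it through.** **Inputs.** Ratio 1:1, blocked by site, size unspecified (protocol 8.2.1); no blinding (8.2.2); 140 randomised subjects at up to 8 sites (7.1). The documents give no predictability figure to reproduce; the 140 is 2 × 70, where 70 = 63 / 0.9 (section 11). Assumptions of this check: even enrolment, as 4 sites of 17 and 4 of 18 (68 + 72 = 140), and a site that knows the block size.

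**Step 1: one block of size 4.** There are six balanced orders. In AABB and BBAA the last two places are certain; in the other four only the last is. Mean certain places = (2 × 2 + 4 × 1) / 6 = 1.333, or 33.3% of the block. Guessing the arm used less so far is right with probability 1/2, 2/3, 2/3 and 1 at the four places: 2.833 / 4 = 70.8%.

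**Step 2: general size 2m.** Certain places per block = 2m/(m+1), a share of 1/(m+1). Guess rates come from exact recursion over the places left.

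| Block size | Certain | Correct guesses | Largest imbalance per site |
|---|---|---|---|
| 2 | 50% | 75.0% | 1 |
| 4 | 33.3% | 70.8% | 2 |
| 6 | 25% | 68.3% | 3 |
| 8 | 20% | 66.6% | 4 |
| 12 | 14.3% | 64.3% | 6 |
| 18 | 10% | 62.2% | 9 |

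No size listed reaches 0% certain or the 50% of chance guessing. A block of 18, about a whole site, still leaves 10% certain and allows an imbalance of 9 at a site (8 × 9 = 72 over 8 sites), which defeats the balance demand.

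**Step 3: this trial, allowing for incomplete last blocks.**
- Size 4: each site completes 4 blocks, and the 1 or 2 places left over are never certain. 8 × 4 × 1.333 = 42.7.
- Size 6: a site of 18 completes 3 blocks, 3 × 1.5 = 4.5. A site of 17 completes 2 and stops one short in the third; the missing place is the one always certain, so 2 × 1.5 + (1.5 − 1) = 3.5. 4 × 4.5 + 4 × 3.5 = 32.0.
- Size 8: each site completes 2 blocks, and the 1 or 2 places left over are never certain. 8 × 2 × 1.6 = 25.6.

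Simulation agrees: 42.6, 32.0 and 25.6.

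**Step 4: randomly varying sizes.** Same sites, by simulation, against an optimal guesser who knows the set of sizes but not their order. The size sets are assumptions.

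| Scheme | Certain, of 140 | Best-guess accuracy |
|---|---|---|
| Single size 4 | 42.6 (30.4%) | 69.6% |
| Single size 6 | 32.0 (22.9%) | 67.4% |
| Single size 8 | 25.6 (18.3%) | 65.4% |
| Varying {2,4,6} | 5.0 (3.6%) | 69.2% |
| Varying {4,6} | 8.4 (6.0%) | 68.0% |
| Varying {4,6,8} | 3.4 (2.4%) | 66.7% |

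Varying the size removes most certain predictions. It hardly changes best-guess accuracy.

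**The case against.** **The protocol never says that the size is fixed.** This stands. The sentence states an aim for a schedule still to be generated, and a list with varying sizes would not contradict it. A reader might infer that a single fixed size was chosen; the documents do not show that. They show that size is the only means named and that nothing provides for variation or non-disclosure.

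**Foresight is conditional.** This also stands. The protocol does not tell sites the size, so the step 3 counts are a worst case. A reader might infer that investigators could foresee allocations as a matter of course. The text supports only that a site that knows or works out the size could foresee some of them.

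**The counts could be put higher or lower.** One third, one quarter and one fifth of 140 would be 47, 35 and 28, but that assumes that every block is completed, which sites of 17 or 18 do not allow. Enrolment is competitive (section 10.2), so even site sizes are an assumption and the true counts depend on how sites recruit.

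**There are other safeguards.** The network system hides the list until consent and eligibility are settled. Section 7.4 asks for consecutive screening with logged reasons for exclusion, and section 8.5.1 for retained screening records. These make selection harder to conceal. They do not stop inference from past allocations or fix the order in which waiting subjects are randomised.

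**The route to bias is narrow.** Exclusions 4, 13 and 14 also involve judgement, but only exclusion 10 plausibly tracks the difficulty of the index knee. Nor can it be said that no analysis could help: pre-operative alignment is recorded (sections 9.1.2 and 9.2.1), so imbalance on it could be examined and adjusted for. Unrecorded aspects of difficulty could not.

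**No result depends on it.** SAP section 2 reports termination with four subjects enrolled, and section 7.10 has no primary analysis. This limits the practical consequence but does not rescue the design.

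**Conclusion.** The concern holds as a point about the protocol's design. Section 8.2.1 asks of block size a property that no single size has in an open trial blocked by site. For sizes 4, 6 and 8 about 43, 32 and 26 of 140 allocations would be certain in advance, given 8 sites of 17 or 18 subjects and a site that knows or infers the size. This is more than a missing detail, because applying the rule as written with one size would leave those allocations open to prediction. The documents do not support saying that a fixed size was adopted, that sites did foresee allocations, or that any subject was selected on that basis. It is a real weakness with a cheap remedy and is not fatal to the design.

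**What to change.** Replace the block-size sentence in section 8.2.1 with text to this effect: *Allocation will use permuted blocks of randomly varying size within each site. The block sizes and the schedule will be held by the generating statistician and withheld from sites and from the site-facing study team.* Drop the statement that size makes the next treatment unguessable. The network-based system in section 8.5.2 needs only the new list.

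The gain should be described accurately: far fewer certain predictions, but still better-than-chance guessing (step 4). The remedy also does not touch the eligibility re-check before surgery (section 9.1.3), which takes place after randomisation.

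Costs are a setting in the randomisation list and slightly looser balance if the study stops mid-block: the largest imbalance at a site is half the largest block, so 3 for {4,6} or 4 for {4,6,8}, against 2 for a single size of 4. A protocol amendment is also needed, with approval by the signatories and the IRB or IEC (section 16). As this trial has ended, the change matters for any restart or reuse of the wording.

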### 8.2.2 Blinding

The study is non-blinded.

## 8.3 DATA MANAGEMENT

This study utilizes a validated, encrypted electronic data capture system that is 21 CFR Part 11 compliant. Access to the electronic data capture system is restricted by study role in accordance with Smith and Nephew procedures.

A Data Management Plan (DMP) is written according to Smith and Nephew procedures containing details of the data management process. The following is a brief description of the key points detailed in this plan.

### 8.3.1 Data Review and Quality Assurance

Data will be transcribed from the data source to an electronic Case Report Form (eCRF). All data requested on the eCRFs are considered required. Data points not collected and/or recorded will be considered deviations unless otherwise specified.

Data collection is the responsibility of the clinical trial staff at the site under the supervision of the Principal Investigator. The Principal Investigator is responsible for ensuring the accuracy, completeness, legibility, and timeliness of the data reported. The Principal Investigator must provide his/her electronic signature on the appropriate eCRFs to be documented in compliance with local regulations. Changes to data previously submitted to the sponsor will require a new signature by the Investigator to acknowledge/approve the changes.

Visual and computer data review will be performed in line with Smith and Nephew procedures to identify possible data discrepancies. Manual and automatic queries will be created within the electronic data capture system, and will be issued by Smith and Nephew to the site for appropriate response. Site staff are responsible for resolving all queries in the electronic data capture system.

### 8.3.2 Retention Period

All eCRFs will be archived once the study is completed and will be kept for a period of no less than five years after the later of the following dates: the date of which the study is terminated or completed or; the date that the records are no longer required supporting marketing applications.

## 8.4 STUDY ENDPOINTS

### 8.4.1 Primary Endpoint

The primary endpoint of this study is defined as the evaluation of the proportion of subjects achieving planned post-operative leg alignment. Achieved leg alignment is defined as  $\pm 3^\circ$  from the subject's specific target in comparison with conventional manual instrumentation.

### 8.4.2 Secondary Endpoints

The following secondary endpoints have been defined for this study in order to evaluate the safety and performance of CORI in comparison with conventional manual instrumentation up to 12 months post-operatively:

- Component Alignment
- Radiographic assessment (Presence of radiolucent lines, osteolysis & implant migration)
- 2011 Knee Society Score (2011 KSS)
- Oxford Knee Score (OKS)
- Forgotten Joint Score (FJS-12)
- Five-level EuroQol five-dimensional (EQ-5D-5L) VAS & index scores

### 8.4.3 Other Endpoints

The following additional endpoints have been defined for this study:

#### CONFIDENTIAL AND PROPRIETARY

This document contains information that is confidential and proprietary to Smith & Nephew PLC and Smith & Nephew, Inc. and is intended for use only by Smith+Nephew and its manufacturer. It shall not be reproduced or copied in whole or in part, nor shall the contents be disclosed by any means without prior written permission from Smith+Nephew, nor shall anyone make any use of it that is contrary to the expressed or implied wishes of Smith+Nephew.

Clinical Protocol	Study Number: CORI.2019.06
A Prospective, Multi-center, Randomized Controlled Study to Evaluate the Safety and Effectiveness of REAL INTELLIGENCE™ CORI™ in unicondylar knee arthroplasty (UKA) Procedure	Version: 4.0-Master, 07 Sep 2022
	Page: 58 of 167

- Leg alignment pre- and post-cementation for CORI UKA
- Navigations System time as extracted from the Subject's CORI Case Report generated by the CORI Software.
- Cutting time of the robotic drills extracted from the Subject's CORI Case Report, generated by the CORI Software.

#### **8.4.4 Safety Endpoints**

Safety endpoints include the collection of the following events:

- All adverse events (AEs) and complications occurring from the time of subject enrollment until study termination or study completion including intra-operative adverse events and complications.
- Device related re-intervention
- Device Deficiencies
- Knee implant revision rate

### **8.5 METHODS USED TO MINIMIZE BIAS AND MAXIMIZE VALIDITY**

#### **8.5.1 Multiple sites**

After fulfillment of all eligibility criteria (including informed consent), subjects will be enrolled and randomized at multiple sites, utilizing up to 8 sites in total for the study. Subject enrollment will continue until the completion of recruitment of a minimum of 140 subjects. File records and enrollment registration forms for screening work must be retained and submitted to the Sponsor as needed.

#### **8.5.2 Prospective Consecutive Enrolment**

Subjects meeting all inclusion/exclusion criteria will be randomly allocated to one of two treatment groups (CORI Navigational versus conventional manual instrumentation) in a 1:1 allocation ratio. Blocked randomization to balance this allocation ratio by investigational site and overall will be implemented through a

